#### **Rescue Medication Use Within 24 Hours Post-Dose**

Rescue medication use within 24 hours post-dose is defined as time to rescue medication use  $\leq$  24 hours.

Treatment group comparisons of the percentage of subjects using rescue medication within 24 hours post-dose will use analogous methods as the principal analysis of the co-primary endpoint of pain freedom, except that the NC=F and RM=F methods will not be applied because they are not applicable to this endpoint (see Section 6.3.3.1).

## **Time to Rescue Medication Use Through 24 Hours Post-Dose**

Time to rescue medication use through 24 hours post-dose will be assessed by treatment group as follows:

- Kaplan-Meier (KM) plot and table using 2-hour time intervals (i.e., 0 to 2, > 2 to 4, ..., > 24). The KM plot will display the percentage of subjects taking rescue medication within 24 hours post-dose on the y-axis versus time in hours on the x-axis.
- Time-to-event distribution table (hours), including a log-rank p-value (BHV-3500 versus placebo).

See Section 7.1.1.1 for time-to-event plot and table attributes. Rescue medication use through 24-hours post-dose will be considered as an event in these time-to-event analyses. Subjects who do not take rescue medication within 24 hours post-dose will be censored at 24 hours and 1 minute (i.e., 1441 minutes).

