### 2.2 Randomization Methodology

Per protocol, subjects in this study may be randomized only once.

The study will randomize approximately 1,600 subjects. The subjects will be randomized in a 1:1:1:1 ratio across 4 treatment groups (BHV-3500 5 mg, BHV-3500 10 mg, BHV-3500 20 mg, or placebo); see Figure 1. The randomization will be stratified by prophylactic migraine medication use (yes or no).

[figure not shown]

Figure 1: Study Schematic

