#### 6.3 Efficacy

Efficacy analyses will be based on mITT subjects by as-randomized treatment group only (excluding All BHV-3500 and overall).

Treatment comparisons of binary endpoints will be stratified by prophylactic migraine medication use at randomization except within subgroups. If a single cell has sparse data (< 5 subjects), then the analysis will be performed pooled across strata.

All CIs will be two-sided. In treatment comparisons of binary endpoints, CIs will be based on a normal approximation to the binomial distribution using asymptotic standard error (ASE). In descriptive analyses of binary endpoints, exact Clopper-Pearson CIs will be used. Otherwise, CIs for continuous endpoints will be based on the normal distribution.

A by-subject listing of eDiary migraine characteristics will be provided for randomized subjects that displays parameters listed in Section 7.6.3.2 at migraine attack onset and over time post-dose. The rescue medication start date/time and time to rescue medication use in hours will also be included (see Sections 6.3.4.3 and 7.3); data collected on or after the rescue medication start date/time will be flagged.

Post-dose efficacy data will be slotted into analysis windows automatically by the eDiary (see Section 7.6.3.2). All efficacy endpoints will be assessed using analysis windows, unless specified otherwise.

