# **Time-to-Event Efficacy Endpoints**

The following time-to-event endpoints will be analyzed:

- Pain freedom through 4 hours post-dose
- Pain freedom through 8 hours post-dose
- MBS freedom through 8 hours post-dose for subjects with MBS reported at on-study migraine attack onset
- Pain relief through 4 hours post-dose
- Pain relief through 8 hours post-dose
- Nausea freedom through 8 hours post-dose for subjects with nausea present at on-study migraine attack onset
- Phonophobia freedom through 8 hours post-dose for subjects with phonophobia present at on-study migraine attack onset
- Photophobia freedom through 8 hours post-dose for subjects with photophobia present at onstudy migraine attack onset
- Return to normal function through 8 hours post-dose for subjects with functional disability at on-study migraine attack onset.

Analyses are based on non-missing, post-dose efficacy data relevant to each endpoint.

For a given time-to-event endpoint, subjects are considered to have an event through X hours (X = 4 or 8) if the first post-dose eDiary finding date/time defining response is (1) at or before the upper bound of the X-hour analysis window in minutes (see Table 5), and (2) is before the imputed rescue medication start date/time, if not missing (see Section 7.3).

Otherwise, subjects who do not have an event through X hours will be censored at the earliest of the following: (1) upper bound of the X-hour analysis window + 1 minute; (2) time from the study drug start date/time to the imputed rescue medication start date/time, if the time is at or before the upper bound of the X-hour analysis window in minutes; (3) time from the study drug start date/time to the last non-missing finding date/time defining the endpoint, if the time was before the lower bound of X-hour analysis window in minutes.

For each endpoint listed above, time to event will be assessed by treatment group as follows:

- KM plot and table using the following time intervals post-dose: 0 to 15, >15 to 30, > 30 to 45, > 45 to 60, > 60 to 90, > 90 to 120, > 120 to 180, > 180 to 240, > 240 to 360, > 360 to 495, and > 495 minutes. The KM plot will display the percentage of subjects with the event on the y-axis versus time in minutes on the x-axis. See Section 7.1.1.1 for KM plot and table attributes.
- Time-to-event distribution table (minutes), including a log-rank p-value (BHV-3500 versus placebo).

See Section 7.1.1.1 for time-to-event plot and table attributes.

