### 7.1.1.1 Time-to-Event Tables and Plots

Time-to-event endpoints will be summarized with KM tables displaying the following at each time interval:

- Number of subjects at risk, defined as those who did not have the event just prior to the start of the interval and who were not censored prior to the interval
- Number of subjects with events, defined as those who had the event for the first time during the interval
- Number of subjects censored, defined as those who did not have the event and whose censoring date/time is in the interval
- Cumulative probability of having the event with lower and upper CI limits, based on the KM product limit method.

Time-to-event endpoints will also be summarized with corresponding KM plots displaying 100 times the cumulative probability of having the event on the y-axis and time on the x-axis, including the number of subjects at risk at each time point below the x-axis.

Time-to-event distributions of endpoints will be summarized with the following descriptive statistics: number and percentage of subjects with events; number and percentage of subjects censored in or before the last time interval; number and percentage of subjects censored in the last time interval; median time to event with CI using the method of Brookmeyer and Crowley.

CI levels will be 98.3% for efficacy endpoints and 95% for all other endpoints.

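### The SAP states no stratification for its log-rank tests, although randomization and the companion binary comparisons use prophylactic medication strata; stratifying them would be a free, small improvement.

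*SAP*

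**What the plan says.** SAP 2.2 sets the design: "The randomization will be stratified by prophylactic migraine medication use (yes or no").

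SAP 6.3 carries that factor into the analysis for one class of endpoint: "Treatment comparisons of binary endpoints will be stratified by prophylactic migraine medication use at randomization except within subgroups". An exception follows directly: "If a single cell has sparse data (< 5 subjects), then the analysis will be performed pooled across strata".

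In SAP 6.3.4.3 the 24-hour rescue percentage follows the binary rule: "Treatment group comparisons of the percentage of subjects using rescue medication within 24 hours post-dose will use analogous methods as the principal analysis" of pain freedom, which is a stratified CMH test. The time-to-rescue analysis beneath it asks for a distribution table in hours, "including a log-rank p-value (BHV-3500 versus placebo").

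SAP 6.3.5.2 lists nine time-to-event efficacy endpoints and asks for the same output: "Time-to-event distribution table (minutes), including a log-rank p-value (BHV-3500 versus placebo").

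The conventions in SAP 7.1.1.1 begin "Time-to-event endpoints will be summarized with KM tables displaying the following at each time interval" and go on to risk sets, censoring counts, medians and confidence levels. They do not mention strata.

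**The concern.** When randomization is stratified, the usual practice is to carry the factor into the analysis. The SAP does this for binary comparisons and is silent for log-rank tests. Ten time-to-event endpoints (one for rescue, nine for efficacy) by three doses give 10 × 3 = 30 p-values whose relation to the randomization factor is unstated.

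Two things are at stake, both modest. First, if prophylaxis use predicts outcome, an unstratified test gives up a little power. Second, two programmers could reasonably produce different p-values from the same text. The rescue endpoint shows this best: the percentage comparison and the log-rank test use the same evaluable subjects, event and 24-hour horizon, yet only the first is tied to the randomization stratum.

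**Working it through.** **1. The plan's own power figure.** The documents give no power, event count or effect size for any log-rank test. Their only power statement (Protocol 9.2, SAP 5) concerns the co-primary endpoints: 380 per arm, alpha 0.0167. It was checked as

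power = Φ{[d − z·√(2p̄(1−p̄)/n)] / √[(p₁(1−p₁)+p₂(1−p₂))/n]}, with z = 2.393 (two-sided).

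- Pain freedom, 22% v 12%: (0.10 − 2.393 × 0.02725)/0.02701 = 1.288, giving 90.1%.
- MBS freedom, 45% v 32%: (0.13 − 2.393 × 0.03530)/0.03498 = 1.301, giving 90.3%.
- Joint, if independent: 0.901 × 0.903 = 81.4%.

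The stated 90%, 90% and roughly 80% reproduce. They do not depend on the log-rank choice.

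**2. The two tests.** Unstratified: Z = Σ(O−E)/√ΣV over all subjects. Stratified: O−E and V are computed within each prophylaxis stratum and then summed.

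**3. 24-hour simulation (the rescue setting).** From the documents: 380 per arm, censoring just after 24 hours, alpha 0.0167. Assumed: two-sided test, exponential times, strata balanced between arms, placebo 24-hour rescue rate 35%, treatment hazard ratio 0.65. The prophylaxis share and stratum hazard ratio were varied, with 3,000 trials per setting. Power in %, unstratified → stratified:

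| Stratum HR | 10% on prophylaxis | 20% | 40% |
|---|---|---|---|
| 1.0 | 78.7 → 78.7 (0.0) | 79.8 → 79.9 (+0.1) | 79.6 → 79.5 (−0.2) |
| 1.5 | 79.3 → 79.5 (+0.2) | 79.6 → 79.8 (+0.2) | 79.7 → 80.3 (+0.5) |
| 2.0 | 80.3 → 80.9 (+0.6) | 78.6 → 79.5 (+1.0) | 78.8 → 80.0 (+1.2) |
| 3.0 | 77.4 → 80.3 (+3.0) | 75.9 → 79.5 (+3.6) | 75.7 → 79.9 (+4.1) |

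Differences are taken before rounding. The two tests reached the same decision in 95.4% to 99.9% of these trials.

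**4. Null behaviour, same setting with treatment hazard ratio 1.** Rejection ranged from 0.9% to 2.0% unstratified and from 1.3% to 2.2% stratified, against a nominal 1.67% (standard error √(0.0167 × 0.9833/3000) = 0.23 points). At stratum hazard ratio 3, averaging the three shares gives (1.30 + 0.90 + 1.47)/3 = 1.22% unstratified and (1.70 + 1.60 + 2.07)/3 = 1.79% stratified, with standard error √(0.0167 × 0.9833/9000) = 0.14 points. The unstratified test is therefore mildly conservative when the stratum is strongly prognostic, and nothing suggests inflation.

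**5. 8-hour simulation (the efficacy setting).** Assumed: control hazard 0.12 per hour, treatment hazard ratio 1.25, two-sided 0.05, 4,000 trials, 380 per arm.

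- 20% on prophylaxis, stratum hazard ratio 0.7: 67.7% → 67.9%, a gain of 0.2 points.
- 40% on prophylaxis, stratum hazard ratio 0.5: 59.9% → 63.1%, a gain of 3.2 points.

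**The case against.** The strongest reply is that an unstratified log-rank test is valid, that these p-values are supportive, and that stratifying is a preference. Much of this stands, and it rules out several stronger readings.

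- **That the SAP chose unstratified tests.** It does not say so. It uses that word for the subgroup analyses in 6.3.3.1 and 6.3.3.2, but never for a log-rank test. Unstratified is the default reading of silence.
- **That every overall binary comparison is stratified.** The sparse-cell pooling rule in 6.3 is an exception.
- **That a confirmatory conclusion is at risk.** The hierarchy (SAP 1.2.2 and 6.1.2) tests the probability of rescue, third among the secondaries, not the time to it. SAP 6.3.5 labels exploratory efficacy p-values descriptive. The time-to-rescue p-value has no such label, but it is outside the hierarchy too.
- **That strata alone could separate the binary and log-rank results.** For rescue, the log-rank test also uses event times. For the nine efficacy endpoints, 6.3.5.2 takes the first response and censors at rescue, while the binary analyses use one time point and count rescue and missing data as failure. Stratifying will not make them match.
- **That precision is always lost.** The documents nowhere say that prophylaxis use predicts outcome. If it does not, power moves by −0.2 to +0.1 points, which is nothing of substance.

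The reply does not remove the gap in specification. Nor does it give a reason to leave the factor out, since stratifying costs essentially nothing when the factor is uninformative.

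**Conclusion.** The point holds as a minor gap with a free improvement. No stratification is stated for any log-rank test, and the default would be a valid test that is slightly conservative if the stratum is prognostic. The likely gain is small: about 1 point of power or less for most settings with a stratum hazard ratio up to 2 at 24 hours (at most 1.2 points). It reaches 3 to 4 points only for a strongly prognostic stratum (hazard ratio 3 at 24 hours, or 0.5 with 40% on prophylaxis at 8 hours). These sizes rest on assumed event rates, treatment effects, prophylaxis shares and stratum effects. The co-primary and hierarchical secondary conclusions are untouched.

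**What to change.** In SAP 7.1.1.1, add a sentence stating that each dose-versus-placebo log-rank test is stratified by prophylactic migraine medication use at randomization (the IWRS stratum), with the same pooling rule for sparse cells as in 6.3. The rule matters here because several of these endpoints are limited to subjects with a given symptom or disability at onset. Refer to the sentence from 6.3.4.3 and 6.3.5.2. Leave the Kaplan-Meier curves and tables unstratified.

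The cost is one sentence, two cross-references and one strata variable in the program. The stratum is already held as a baseline characteristic (SAP 6.2.4.1), so no new data are needed. It should be settled before unblinding, so that no one chooses between two available p-values.

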# 6.3.4.4 Freedom from Photophobia, Phonophobia or Nausea at 2 Hours Post-

Freedom from each symptom (nausea, phonophobia, photophobia) at 2 hours post-dose will be assessed separately.

Symptom freedom is defined as a symptom absent at a single time point post-dose for subjects with the symptom present at on-study migraine attack onset. Thus, all analyses of symptom freedom will be based on mITT subjects with the symptom present at on-study migraine attack onset (see Section 7.6.3.2), e.g., nausea freedom at a post-dose time point will be based on subjects with nausea present at onset.

Symptom freedom outcomes at 2 hours post-dose will be summarized by treatment group (see Section 6.3.5.2).

Treatment group comparisons of the percentage of subjects with symptom freedom at 2 hours post-dose will use analogous methods as the principal analysis of the co-primary endpoint of pain freedom with NC=F and RM=F (see Section 6.3.3.1).

#### 6.3.4.5 Sustained Pain Relief from 2 to 24 Hours Post-Dose

Sustained pain relief from 2 to 24 hours post-dose is defined as pain level of none or mild at all time points from 2 to 24 hours post-dose.

Subjects who meet all of the following criteria will be classified as responders:

- Pain level of none or mild at all time points from 2 to 24 hours post-dose, i.e., in the 2 to 24-hour post-dose analysis windows
- Missing data at  $\leq 1$  time point from 3 to 8 hours post-dose, i.e., in the 3, 4, 6, or 8-hour post-dose analysis windows
- No intervening rescue medication taken at or before 24 hours post-dose, i.e., rescue medication start date/time missing or > {eDiary finding date/time in the 24-hour post-dose analysis window}.

Otherwise, subjects who are not responders and have any of the following will be classified as failures:

- Intercurrent event: Rescue medication taken at or before 24 hours post-dose (RM=F), i.e., (rescue medication start date/time study drug start date/time) ≤ 25 hours, the upper bound of the 24-hour post dose analysis window
- Moderate or severe pain at any time point from 2 to 24 hours post-dose, i.e., in the 2, 3, 4, 6, 8 or 24-hour post-dose analysis window
- Missing pain level at 2 or 24 hours post-dose (NC=F), i.e., in the 2 or 24-hour post-dose analysis window
- Missing pain level at > 1 time point from 3 to 8 hours post-dose (NC1=F), i.e., in the 3, 4, 6, or 8-hour post-dose analysis window.

Sustained pain relief from 2 to 24 hours outcomes will be summarized by treatment group as the number and percentage of subjects in the following categories:

• Responder: mild or no pain at all time points from 2 to 24 hours post-dose, missing data at ≤ 1 time point from 3 to 8 hours post-dose, and no intervening rescue medication taken at or before 24 hours post-dose

#### Failure

- o Rescue medication taken at or before 24 hours post-dose (RM=F)
- o Moderate or severe pain at any time point from 2 to 24 hours post-dose
  - Severe pain
  - Moderate pain
- o Missing pain level at 2 or 24 hours post-dose (NC=F)
- $\circ$  Missing pain level at > 1 time point from 3 to 8 hours post-dose (NC1=F).

Failure subcategories are mutually exclusive, because subjects who meet more than 1 failure criterion will be classified according to the first failure criterion met; in case of ties, the first failure subcategory that is met in the hierarchy above will be chosen.

Treatment group comparisons of the percentage of subjects with sustained pain relief from 2 to 24 hours post-dose will use analogous methods as the principal analysis of the co-primary endpoint of pain freedom with NC=F, NC1=F, and RM=F (see Section 6.3.3.1).

### 6.3.4.6 Sustained Pain Relief from 2 to 48 Hours

Sustained pain relief from 2 to 48 hours post-dose is defined as pain level of none or mild at all time points from 2 to 48 hours post-dose.

Subjects who meet all of the following criteria will be classified as responders:

- Pain level of none or mild at all time points from 2 to 48 hours post-dose, i.e., in the 2 to 48-hour post-dose analysis windows
- Missing data at ≤ 1 time point from 3 to 8 hours post-dose, i.e., in the 3, 4, 6, or 8-hour post-dose analysis windows
- No intervening rescue medication taken at or before 48 hours post-dose, i.e., rescue medication start date/time missing or > {eDiary finding date/time in the 48-hour post-dose analysis window}.

Otherwise, subjects who are not classified as responders and have any of the following will be classified as failures:

- Intercurrent event: Rescue medication taken at or before 48 hours post-dose (RM=F), i.e., (rescue medication start date/time study drug start date/time) ≤ 49 hours, the upper bound of the 48-hour post dose analysis window
- Moderate or severe pain at any time point from 2 to 48 hours post-dose, i.e., in the 2, 3, 4, 6, 8, 24, or 48-hour post-dose analysis window
- Missing pain level at 2, 24, or 48 hours post-dose (NC=F), i.e., in the 2, 24, or 48-hour post-dose analysis window

• Missing pain level at > 1 time point from 3 to 8 hours post-dose (NC1=F), i.e., in the 3, 4, 6, or 8-hour post-dose analysis window.

Sustained pain relief from 2 to 48 hours outcomes will be summarized for mITT subjects by treatment group as the number and percentage of subjects in the following categories:

- Responder: mild or no pain at all time points from 2 to 48 hours post-dose, missing data at ≤ 1 time point from 3 to 8 hours post-dose, and no intervening rescue medication taken at or before 48 hours post-dose
- Failure
  - o Rescue medication taken at or before 48 hours post-dose (RM=F)
  - o Moderate or severe pain at any time point from 2 to 48 hours post-dose
    - Severe pain
    - Moderate pain
  - o Missing pain level at 2, 24, or 48 hours post-dose (NC=F)
  - $\circ$  Missing pain level at > 1 time point from 3 to 8 hours post-dose (NC1=F).

Failure subcategories are mutually exclusive, because subjects who meet more than 1 failure criterion will be classified according to the first failure criterion met; in case of ties, the first failure subcategory in the hierarchy above will be chosen.

Treatment group comparisons of the percentage of subjects with sustained pain relief from 2 to 48 hours post-dose will use analogous methods as the principal analysis of the co-primary endpoint of pain freedom with NC=F, NC1=F, and RM=F (see Section 6.3.3.1).

#### 6.3.4.7 Sustained Pain Freedom from 2 to 24 Hours

Sustained pain freedom from 2 to 24 hours post-dose is defined as pain level of none at all time points from 2 to 24 hours post-dose.

Subjects who meet all of the following criteria will be classified as responders:

- Pain level of none at all time points from 2 to 24 hours post-dose, i.e., in the 2 to 24-hour post-dose analysis windows
- Missing data at ≤ 1 time point from 3 to 8 hours post-dose, i.e., in the 3, 4, 6, or 8-hour post-dose analysis windows
- No intervening rescue medication taken at or before 24 hours post-dose (see Section 6.3.4.5).

Subjects who are not classified as responders and have any of the following will be classified as failures:

• Intercurrent event: Rescue medication taken at or before 24 hours post-dose (RM=F; see Section 6.3.4.5)

- Mild, moderate or severe pain at any time point from 2 to 24 hours post-dose, i.e., in the 2, 3, 4, 6, 8 or 24-hour post-dose analysis window
- Missing pain level at 2 or 24 hours post-dose (NC=F), i.e., in the 2 or 24-hour post-dose analysis window
- Missing pain level at > 1 time point from 3 to 8 hours post-dose (NC1=F), i.e., in the 3, 4, 6, or 8-hour post-dose analysis window.

Sustained pain freedom from 2 to 24 hours outcomes will be summarized by treatment group as the number and percentage of subjects in the following categories:

- Responder: no pain at all time points from 2 to 24 hours post-dose, missing data at ≤ 1 time point from 3 to 8 hours post-dose, and no intervening rescue medication taken at or before 24 hours post-dose
- Failure
  - o Rescue medication taken at or before 24 hours post-dose (RM=F)
  - Mild, moderate or severe pain at any time point from 2 to 24 hours post-dose
    - Severe pain
    - Moderate pain
    - Mild pain
  - Missing pain level at 2 or 24 hours post-dose (NC=F)
  - $\circ$  Missing pain level at > 1 time point from 3 to 8 hours post-dose (NC1=F).

Failure subcategories are mutually exclusive, because subjects who meet more than 1 failure criterion will be classified according to the first failure criterion met; in case of ties, the first failure subcategory that is met in the hierarchy above will be chosen.

Treatment group comparisons of the percentage of subjects with sustained pain freedom from 2 to 24 hours post-dose will use analogous methods as the principal analysis of the co-primary endpoint of pain freedom with NC=F, NC1=F, and RM=F (see Section 6.3.3.1).

### 6.3.4.8 Sustained Pain Freedom from 2 to 48 Hours

Sustained pain freedom from 2 to 48 hours post-dose is defined as pain level of none at all time points from 2 to 48 hours post-dose.

Subjects who meet all of the following criteria will be classified as responders:

- Pain level of none at all time points from 2 to 48 hours post-dose, i.e., in the 2 to 48-hour post-dose analysis windows
- Missing data at ≤ 1 time point from 3 to 8 hours post-dose, i.e., in the 3, 4, 6, or 8-hour post-dose analysis windows
- No intervening rescue medication taken at or before 48 hours post-dose (see Section 6.3.4.6).

Subjects who are not classified as responders and have any of the following will be classified as failures:

- Intercurrent event: Rescue medication taken at or before 48 hours post-dose (RM=F; see Section 6.3.4.6)
- Mild, moderate or severe pain at any time point from 2 to 48 hours post-dose, i.e., in the 2, 3, 4, 6, 8, 24, or 48-hour post-dose analysis window
- Missing pain level at 2, 24, or 48 hours post-dose (NC=F), i.e., in the 2, 24, or 48-hour post-dose analysis window
- Missing pain level at > 1 time point from 3 to 8 hours post-dose (NC1=F), i.e., in the 3, 4, 6, or 8-hour post-dose analysis window.

Sustained pain freedom from 2 to 48 hours outcomes will be summarized for mITT subjects by treatment group as the number and percentage of subjects in the following categories:

- Responder: no pain at all time points from 2 to 48 hours post-dose, missing data at ≤ 1 time point from 3 to 8 hours post-dose, and no intervening rescue medication taken at or before 48 hours post-dose
- Failure
  - o Rescue medication taken at or before 48 hours post-dose (RM=F)
  - o Mild, moderate or severe pain at any time point from 2 to 48 hours post-dose
    - Severe pain
    - Moderate pain
    - Mild pain
  - o Missing pain level at 2, 24, or 48 hours post-dose (NC=F)
  - $\circ$  Missing pain level at > 1 time point from 3 to 8 hours post-dose (NC1=F).

Failure subcategories are mutually exclusive, because subjects who meet more than 1 failure criterion will be classified according to the first failure criterion met; in case of ties, the first failure subcategory that is met in the hierarchy above will be chosen.

Treatment group comparisons of the percentage of subjects with sustained pain freedom from 2 to 48 hours post-dose will use analogous methods as the principal analysis of the co-primary endpoint of pain freedom with NC=F, NC1=F, and RM=F (see Section 6.3.3.1).

